#### The exclusion criteria are:

- 1. Patients that did not or will not receive the allocated pre-operative surgical preparation solution due to a medical contraindication.
- 2. Received previous surgical debridement or management of their open fracture at a non-participating hospital or clinic.
- 3. Open fracture managed outside of the participating orthopaedic service (e.g., hand fracture managed by plastic surgeon).
- 4. Chronic or acute infection at or near the fracture site at the time of initial fracture surgery.
- 5. Burns at the fracture site.
- 6. Incarceration.
- 7. Expected injury survival of less than 90 days.
- 8. Terminal illness with expected survival less than 90 days.
- 9. Previous enrollment in a PREP-IT trial.
- 10. Currently enrolled in a study that does not permit co-enrollment.
- 11. Unable to obtain informed consent due to language barriers.
- 12. Likely problems, in the judgment of study personnel, with maintaining follow-up with the patient.
- 13. Excluded due to sampling strategy.

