## 4.3 Recruitment Strategy

## 4.3.1 Patient Screening and Consent

Patients 18 years of age or older who present to a recruiting hospital for treatment of an open fracture will be screened for participation within 3 weeks of their fracture. To screen patients presenting with an open fracture(s) for eligibility, designated study personnel at each clinical site will develop a patient enrollment plan. This plan will typically consist of daily participation in orthopaedic patient rounds and a review of daily listings of hospital admissions for patients with open fractures. Upon identification, the study personnel will screen the patient for eligibility and if eligible, approach them for informed consent. Study participants must be enrolled within 3 weeks of their fracture(s) and enrollment may take place at any time within this window. If the patient is unable to provide informed consent (e.g., due to their injury) at the time they were initially identified, informed consent may be delayed until they are able to provide informed consent. Alternatively, if the patient is unable to provide informed consent, informed consent may be obtained from their proxy, with consent obtained from the patient when/if the patient is able to provide consent. Allowing informed consent from a patient's proxy healthcare decision maker will reduce the risk of recruitment bias against the most severely injured patients. In addition, potentially eligible patients will be approached to participate in the trial, even if they did not receive the correct pre-operative antiseptic skin solution. This is consistent with the intention-to-treat principle (ITT) and is necessary to maintain the prognostic balance achieved during the cluster randomization. All screened patients will be classified as included, excluded, or missed. See Table 2 below for the Schedule of Events.

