## 4.5 Blinding

The orthopaedic team (including the study coordinators) cannot be blinded to the treatment allocation as the antiseptic solutions are visually distinguishable and these individuals need to lead the implementation of the cluster-crossover protocol at their clinical site. The Adjudication Committee Members and data analysts will be blinded to the study treatment. All interpretation of study results will initially be done in a blinded manner by developing two interpretations of the results. One interpretation will assume treatment A is povidone-iodine, the other interpretation will assume it is CHG. Once the data interpretations for each assumption are finalized, the data will be unblinded and the correct interpretation will be accepted.

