## 4.6 Description of the Interventions

## 4.6.1 Initial Run-In Phase

Prior to initiating patient recruitment, each clinical site will begin using their assigned preoperative antiseptic skin solution for eligible open fracture surgeries (run-in period) to ensure that acceptable compliance is met before initiating participant enrollment. Acceptable compliance during the run-in phase will be defined as at least 15 eligible open fracture patients with >90% of eligible patients receiving the allocated antiseptic solution or a minimum of one month in duration. The run-in phase may be extended up to 3 months, as deemed necessary by the CEO Methods Center. Study personnel at each clinical site will document compliance with administering the allocated treatment during the run-in phase and submit this weekly to the CEO Methods Center. Specifically, the weekly reports will include the total number of eligible open fracture patients operated on, the proportion who received the assigned pre-operative antiseptic skin solution, and the proportion who did not receive the assigned pre-operative antiseptic skin solution along with details about the deviations (e.g., name of attending surgeon, solution used, rationale for not using the assigned pre-operative antiseptic skin solution). This portion of the study protocol is for quality assurance during the initial implementation of the trial procedures. Open fracture surgeries reviewed during the run-in phase will not be included in the trial. Similarly, these patients will not be approached for informed consent and no individual patient-level data will be submitted. CEO Methods Center personnel will review the weekly reports with each of the clinical sites and develop strategies, as needed, to ensure acceptable compliance during the run-in phase. This weekly communication will prevent any delays in transitioning to the participant enrollment phase.

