## 4.6.2 First Intervention Phase

Once the initial run-in phase is completed, participant recruitment will begin with the clinical sites continuing to use the same pre-operative antiseptic skin solution for all eligible open fracture surgeries for a two-month period. Patients will receive the initially allocated treatment solution for all of their open fracture management surgeries, including repeat planned surgeries, even if a planned subsequent surgery occurs during a recruitment period using the non-allocated solution. Participating clusters will ideally be able to enroll a minimum of 77 open fracture patients per treatment over the total study recruitment duration, and it is anticipated that most recruiting centers will exceed this minimum goal. Methods Center personnel will continue to monitor compliance

with the assigned pre-operative antiseptic skin solution over the enrollment phase and work collaboratively with the clinical sites to minimize cases in which a patient receives the incorrect solution. These monitoring activities will coincide with site-specific procedures to maintain compliance for all patients, even those requiring multiple surgical procedures. If an open fracture requires multiple surgeries and the correct solution is not applied at each procedure, the patient will remain in the study and be analyzed using the allocated solution (ITT principle).

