major study outcomes by telephone, text, or email contact with the participant or the provided alternate contacts. Given these are standard of care visits and the participants will be receiving ongoing orthopaedic care for their acute fractures, minimal loss to follow-up is expected. Using these techniques, we expect greater than 95% follow-up at 3 months and 90% follow-up at 12 months post-fracture.

Participants will not be deemed lost to follow-up until the 12-month visit is overdue and all attempts to contact the participant have been exhausted. Participants will not be withdrawn from the study if the study protocol was not adhered to (e.g., allocated treatment not received, missed follow-up visits, etc.). The reasons for participants being withdrawn from the study will be documented (e.g., withdrawal of consent or lost to follow up).

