#### 5.2 Statistical Methods

## 5.2.1 Analysis Plan Overview

A detailed statistical analysis plan will be published prior to the completion of the trial. The analysis and reporting of the results will follow the CONSORT guidelines for reporting of both pragmatic trials and cluster-randomization trials. The process of patient enrollment and flow throughout the study will be summarized using a flow-diagram. Patient demographics and baseline outcome variables will be summarized using descriptive summary measures expressed as mean (standard deviation) or median (interquartile range) for continuous variables depending on the distribution, and number (percent) for categorical variables. An ITT principle will be adopted to analyze all outcomes and the unit of analysis will be the individual patients. Missing data will be assumed to be missing at random and will be handled with multiple imputation.

The primary analysis will compare the treatment groups on the SSI outcome and the secondary analysis will compare the unplanned fracture-related reoperation outcome. The secondary comparison will be conducted in accordance with best practice guidelines for secondary analyses. For all models, the results will be expressed as relative measure of effect (odds, risk, or hazard ratios) and corresponding two-sided 95% confidence intervals.

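### Minor: exclusion criterion 1 ties eligibility to the solution allocated at the time, so patients contraindicated to one solution only can enter one arm but not the other; the bias is probably small and its direction is unknown.

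*Combined protocol and SAP*

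**What the plan says.** The first exclusion criterion in section 4.2 removes "Patients that did not or will not receive the allocated pre-operative surgical preparation solution due to a medical contraindication". The allocated solution is whichever one the practice is using in that period; it alternates about every two months (sections 3.1 and 4.4).

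Section 4.3.1 takes a different line on other patients who did not get the allocated solution: "potentially eligible patients will be approached to participate in the trial, even if they did not receive the correct pre-operative antiseptic skin solution". The reason given is that this is "necessary to maintain the prognostic balance achieved during the cluster randomization". After enrolment the plan is equally firm. Where the correct solution is not applied at each procedure, "the patient will remain in the study and be analyzed using the allocated solution (ITT principle") (section 4.6.2), and section 4.8.4 adds that "Participants will not be withdrawn from the study if the study protocol was not adhered to".

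On who applies the criterion, and when: "The orthopaedic team (including the study coordinators) cannot be blinded to the treatment allocation" (section 4.5). Sections 4.3.1 and 7.2 allow enrolment and consent up to three weeks after the fracture, so possibly after surgery.

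On reporting, section 4.3.1 classes every screened patient as included, excluded or missed, and section 5.2.1 says "The process of patient enrollment and flow throughout the study will be summarized using a flow-diagram". The run-in reports in section 4.6.1 ask for the "rationale for not using the assigned pre-operative antiseptic skin solution". The documents do not say that this item continues during enrolment, nor that a contraindication to the solution not in use is recorded.

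**The concern.** Take a patient who is contraindicated to povidone-iodine but not to chlorhexidine gluconate (CHG). In a povidone-iodine period criterion 1 excludes this patient; in a CHG period the same patient is eligible. The reverse holds for a contraindication to CHG. Each arm therefore loses a different group of patients.

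If those groups differ in size or in risk of surgical site infection (SSI), the arms differ at baseline for a reason unrelated to treatment effect. The protections in the plan start too late to help. Intention-to-treat analysis keeps enrolled patients in their arm, the crossover balances hospitals, and the adjusted analysis in section 5.2.4 uses covariates of enrolled patients. None of the six sensitivity analyses concerns who was screened out. Without a record of contraindication to the unused solution, the imbalance could be neither measured nor removed afterwards.

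**Working it through.** **What the plan supplies.** It gives no prevalence of contraindication and no link to SSI, so there is no figure on this point to reproduce. Its design figures set the scale:
- SSI risk is 12.5% with CHG and the target risk ratio is 0.65 (section 5.1). So 12.5% × 0.65 = 8.125%, a difference of 4.375 points.
- The sample is 1,400, and 1,400 × 1.10 = 1,540 (Table 5), or 700 and 770 per arm.
- Alpha is 0.05 (Table 5); confidence intervals are two-sided (section 5.2.1).

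**What has to be assumed.** Let eA and eB be the shares of patients contraindicated only to povidone-iodine and only to CHG. Let k be their SSI risk relative to other patients. The ranges of e and k below are assumptions.

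**Risk ratio seen when there is no true effect** (povidone-iodine versus CHG):

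RR = [(1 − eA − eB + k·eB)/(1 − eA)] ÷ [(1 − eA − eB + k·eA)/(1 − eB)]

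If only povidone-iodine is affected (eA = e, eB = 0), this reduces to RR = 1/(1 + e(k − 1)). If only CHG is affected, it is the reciprocal.

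| e | k = 1 | k = 1.5 | k = 2 | k = 3 |
|---|---|---|---|---|
| 1% | 1.000 | 0.995 | 0.990 | 0.980 |
| 5% | 1.000 | 0.976 | 0.952 | 0.909 |

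With contraindications on both sides the effects partly cancel: eA = 1%, eB = 0.5%, k = 2 gives 0.995. With equal shares and equal risks the ratio is exactly 1.

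**On the absolute scale**, with population risk 12.5% and povidone-iodine affected, other patients have risk 12.5%/(1 + e(k − 1)):
- 1%, k = 2: 12.38% versus 12.50%, a difference of −0.12 points, or about 3% of the design difference.
- 5%, k = 3: 11.36% versus 12.50%, a difference of −1.14 points, or 26% of the design difference.

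**Type I error**, ignoring clustering. SE(log RR) = √(2 × 0.875/(n × 0.125)), which is 0.141 at n = 700 and 0.135 at n = 770. With shift s = ln(RR)/SE, the error is Φ(−1.96 − s) + Φ(−1.96 + s).
- RR 0.990: s = −0.07, giving about 5.1%.
- RR 0.980: s = −0.14 to −0.15, giving 5.2% to 5.3%.
- RR 0.909: s = −0.67 to −0.71, giving 10.3% to 10.9%.

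**If the planned RR of 0.65 is true**, the observed value is 0.65/(1 + e(k − 1)) when povidone-iodine is the contraindicated solution, and 0.65 × (1 + e(k − 1)) when CHG is:
- 1%, k = 2: 0.644 or 0.657.
- 5%, k = 3: 0.591 or 0.715.

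The shift can go either way.

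**The case against.** The strongest reply is that this is an ordinary eligibility choice with a negligible effect. A trial may leave out patients who cannot have the assigned product. Sections 4.6.2 and 4.8.4 govern patients already enrolled, while criterion 1 governs who is enrolled, so the rules do not collide. Contraindication is not among the risk factors listed in section 5.2.4, so k = 1, and hence no bias, is quite possible. The larger figures need both a 5% one-sided share and a tripled risk, and nothing in the documents suggests either. Screening classification and a flow diagram are already planned.

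Most of this stands, and it is why the point is minor. It does not remove the asymmetry. A rule that applied equally in both arms would leave the comparison intact; this one does not. The planned reporting also stops short of splitting these exclusions by allocated solution.

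A reader might infer more, in three ways that the documents do not support:
- **That sections 4.2 and 4.3.1 contradict each other.** They do not, because 4.3.1 is limited to potentially eligible patients. Criterion 1 departs from the reasoning given there, not from its letter.
- **That the rule favours povidone-iodine.** The direction depends on which solution is contraindicated more often and on those patients' risk, and neither is given.
- **That unblinded staff will use the criterion to select patients.** Nothing indicates this. The asymmetry arises even if the criterion is applied perfectly.

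**Conclusion.** The concern holds as a minor design point. Arm-dependent eligibility follows from the wording of criterion 1, and no other part of the plan removes it. That the bias is small is a judgement which the documents cannot confirm. It rests on one-sided contraindication being uncommon, around 1%, with relative risk between 1 and 3. Only a frequent, one-sided and strongly prognostic exclusion would matter. The calculations use simple two-arm formulas, ignore clustering and, where a true effect is assumed, apply the same risk ratio to all patients.

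**What to change.** Make the criterion independent of allocation: exclude patients with a documented contraindication to either study solution. Judge this from pre-operative information and record it for every screened patient in all periods. Report criterion-1 exclusions by allocated solution in the flow diagram. Section 5.1 refers to early trial experience, so patients may already be enrolled under the current wording. For them, add a sensitivity analysis leaving out anyone contraindicated to either solution, as far as that can be established from pre-operative records.

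**Cost.** One eligibility amendment, one more screening item and some extra exclusions from the other arm: 770 × 1% ≈ 8, or 770 × 5% ≈ 39. The weak point is under-recording of contraindications to the solution not in use. If a share q is recorded, the null RR is (1 − eq)/[(1 − e) + e(1 − q)k]. At q = 1 it is 1.000. At q = 0.5 about half the bias remains: 0.995 instead of 0.990 (1%, k = 2), or 0.951 instead of 0.909 (5%, k = 3).

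**Another route, not preferred.** These patients could be enrolled and analysed as allocated, in line with the reasoning of section 4.3.1. That removes the selection but dilutes the effect, even when k = 1. Assume that non-recipients carry the risk of the other study solution and that povidone-iodine is the one contraindicated. Then RR = [0.65(1 − e) + ek]/(1 − e + ek), so 0.65 becomes 0.654 to 0.660 at 1% and 0.668 to 0.698 at 5% (k = 1 to 3). Counting a contraindication to either solution and holding CHG-arm risk at 12.5%, the two-proportion sample size for 80% power rises by about 1-7% at 1% and 8-38% at 5%. This route would also have to be reconciled with three things: the statement in section 4.2 that all open fractures follow the cluster allocation, the same-solution statements in sections 4.6.2 and 4.6.6, and the site adherence thresholds in section 4.6.5.

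Neither route should change which solution a patient is given.

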#### Additional eligibility considerations:

1. Patients with multiple open fractures will be eligible for inclusion. Study personnel will collect data on up to three open fracture regions. In patients with more than three open fracture regions, the treating surgeon will determine the three most severe open fractures.

For each open fracture, the entire injured anatomic region will be included. Therefore, if there are two open fractures that anatomically communicate, they will be considered within the same region (e.g. within the shoulder region, forearm, etc.). Similarly, adjacent closed fractures that anatomically communicate with the open fracture or are treated within the same surgical incision will be included. Common examples of these include forearm fractures, tibia/fibula fractures, and peri-articular fractures. The anatomic joint region, adjacent fractures, and contiguous wounds will be defined at the time of patient enrollment on the case report forms (CRFs).

- 2. All open fractures should be treated as per cluster randomization.
- 3. At the time of screening, patients who are in another study who meet eligibility criteria are to be included in the Aqueous-PREP trial unless the other trial does not permit coenrollment.

## 4.3 Recruitment Strategy

## 4.3.1 Patient Screening and Consent

Patients 18 years of age or older who present to a recruiting hospital for treatment of an open fracture will be screened for participation within 3 weeks of their fracture. To screen patients presenting with an open fracture(s) for eligibility, designated study personnel at each clinical site will develop a patient enrollment plan. This plan will typically consist of daily participation in orthopaedic patient rounds and a review of daily listings of hospital admissions for patients with open fractures. Upon identification, the study personnel will screen the patient for eligibility and if eligible, approach them for informed consent. Study participants must be enrolled within 3 weeks of their fracture(s) and enrollment may take place at any time within this window. If the patient is unable to provide informed consent (e.g., due to their injury) at the time they were initially identified, informed consent may be delayed until they are able to provide informed consent. Alternatively, if the patient is unable to provide informed consent, informed consent may be obtained from their proxy, with consent obtained from the patient when/if the patient is able to provide consent. Allowing informed consent from a patient's proxy healthcare decision maker will reduce the risk of recruitment bias against the most severely injured patients. In addition, potentially eligible patients will be approached to participate in the trial, even if they did not receive the correct pre-operative antiseptic skin solution. This is consistent with the intention-to-treat principle (ITT) and is necessary to maintain the prognostic balance achieved during the cluster randomization. All screened patients will be classified as included, excluded, or missed. See Table 2 below for the Schedule of Events.

**Table 2: Schedule of Events** 

Assessment	Visit 1:	Visit 2:	Visit 3:	Visit 4:	Visit 5:	Visit 6:
	Enrollment	6 weeks	3 months	6 months	9 months	12 months
		post-fracture	post-fracture	post-fracture	post-fracture	post-fracture
Eligibility						
Screening	•					
Informed						
Consent	•					
Collection of						
Demographic						
and Fracture	•					
Characteristics						
Data						
Collection of						
Surgical Data	•					

Assessment	Visit 1:	Visit 2:	Visit 3:	Visit 4:	Visit 5:	Visit 6:
	Enrollment	6 weeks	3 months	6 months	9 months	12 months
		post-fracture	post-fracture	post-fracture	post-fracture	post-fracture
Collection of						
Peri-Operative	•					
Data						
Collection of						
Study Event	•	•	•	•	•	•
(SSI) Data						
Collection of						
Reoperation	•	•	•	•	•	•
Data						
Collection of	_		_			_
SAE Data	•	•	•	•	•	•

Informed consent and enrollment must occur within the 3 weeks (21 days) from the patient's fracture (Day 0 is the date of the fracture).

Visits are to be completed at routine clinic visits. When necessary, visits may also be completed by telephone, text, email, standard mail, and/or a review of the participant's medical record.

Follow-up visit windows touch so that participants will always fall into a specific window. The windows are: 4 to 8 weeks (i.e., 28 to 56 days), 2 to 4.5 months (i.e., 57 to 137 days), 4.5 to 7.5 months (i.e., 138 to 228 days), 7.5 to 12 months (i.e., 229 to 365 days), and greater than 12 months (i.e., 366 to 730 days), respectively, from the participant's fracture.

## 4.3.2 Enrollment Sampling Plan

When the volume of eligible patients exceeds a participating site's ability to effectively enroll and follow all eligible patients, a sampling strategy may be implemented. A sampling strategy is available within the REDCap Cloud electronic data capture (EDC) system which will randomly determine whether an eligible patient should be approached for consent and inclusion in the study. The randomization software will use randomly selected block sizes consistent with the sampling ratio being used during the recruitment periods. Examples of potential random sampling strategies a site may use include:

- 1. For every three eligible patients, there will be one excluded eligible patient (3:1 ratio).
- 2. For every two eligible patients, there will be one excluded eligible patient (2:1 ratio).
- 3. For each eligible patient, there will be one excluded eligible patient (1:1 ratio).
- 4. For each eligible patient, there will be two excluded eligible patients (1:2 ratio).
- 5. For each eligible patient, there will be three excluded eligible patients (1:3 ratio).

The number of eligible patients approached for consent and inclusion in the study, and the number of eligible patients that are excluded due to a sampling strategy will be documented in the EDC system.

